# Threats to Validity

For Aim 1 selection bias and loss-to-follow-up are threats to validity; thus, we will recruit without

Table 2. Power to detect odds ratio for varying												
proportion exposed in clinic arm												
Proportion exposed in clinic												
	arm (e.g., HIV+)											
Odds Ratio	0.4	0.5	0.6									
1.50	0.52	0.52	0.49									
1.75	0.79	0.79	0.75									
2.00	0.93	0.92	0.89									
2.25	0.98	0.98	0.96									

reference to home-based screening or HRA to lessen the population of persons with heightened concern and reservations about self-swabbing or HRA. Recruitment will use diverse strategies to select a broad spectrum of MSM and transpersons. Those strategies will be modified if enrolled persons are not racially and ethnically diverse; however, since study participants may still be different than non-participants we will ask participants about enrollment motivation including potential concern about study procedures like HRA.

For Aim 2 our primary CASI instruments will be adapted from validated cervical cancer screening instruments given the absence of validated anal cancer screening instruments. The CASI format will keep information bias and missing data to a minimum. If there are excessive missing data for a covariate, we will use the SAS procedure MI to impute missing values.

For Aim 3, we are keenly aware that selection bias and loss-to-follow-up are threats to validity; thus, questions during eligibility screening and consenting will capture data on reasons for declining study participation and the baseline CASI will provide rich data on those who do not return at 12 months. Specimen validity may suffer if poorly collected or exposed to extreme temperature, but studies find self-swabs generally have high adequacy.

# PUBLICATION OF RESEARCH FINDINGS

We have budgeted for three publications although we anticipate >12 publications. Community presentations will deliver study results to Milwaukee communities. Presentations of results will occur at HPV-related conferences.

#### ETHICAL AND REGULATORY CONSIDERATIONS

# IRB Approval

The principles of Institutional Review Board (IRB) approval and informed consent described in Department of Health and Human Services (DHHS) regulations for the Protection of Human Subjects regulations (45 CFR Part 46)] must be followed. IRB approval of the protocol and the informed consent form must be given in writing.

The Investigator(s) must receive a copy of the letter of approval from the IRB, which specifically approves the protocol and informed consent, before participant enrollment. The IRB must also approve any significant changes to the protocol and documentation sent to the Investigator(s). The IRB must review the research project at least once every 365 days during the project. Continuing approval of the project must be given in writing and provided to the Investigator(s).

Records of all study review and approval documents must be kept on file by the Investigator and are subject to inspection during or after completion of the study. Adverse events must be reported to the IRB according to local procedures. The IRB should receive notification of completion of the study and final report within 3 months of study completion and termination. The Investigator will maintain an accurate and complete record of all submissions made to the IRB, including a list of all reports and documents submitted.

## Changes to the Protocol

Any change or addition to this protocol requires a written protocol amendment that must be approved by the MCW IRB and the Investigator before implementation. A copy of the written approval of the IRB must be sent to the Investigator.

# Participant Confidentiality

The Investigator will grant monitor(s) and auditor(s) from the NCI and regulatory authorities access to the participants' data. The participant's confidentiality will be maintained and will not be made publicly available to the extent permissible by the applicable laws.

#### Records to be Kept

Information linking the participants' identity to the study ID will be kept in locked file cabinets. Separate cabinets will contain informed consents.

All data will be in password-protected digital format. Names, unique ID number, and contact information will be kept in separate digital files from all other data. All study-related outcome data will only include the unique ID number coded identifiers. All computers will require a password to access files. Computer-assisted self-interviewing will be used so participants can confidentially report sensitive behaviors. No information that could lead to personal identification of participants will be included in any of the reports or given to any non-authorized person. Staff will be trained on how to review electronic medical records for evidence of HIV status and HPV disease and procedures. Medical record data will be entered directly into a digital abstraction form. Laptops will also have strong data encryption installed as per requirements at MCW.

## Specimen Archiving

As an optional procedure to participants, we will store remaining samples in a specimen bank after study testing is complete for future use at the Medical College of Wisconsin and collaborating institutions. They will be stored without any personal information that could link them to a participant. The samples will have a code. The study staff will have the codes linking a participant to the samples stored in a locked, private area. Samples may be used for evaluation of infectious diseases or markers of infection or disease and will not be destroyed until the specimen cannot be used for these purposes. The results of this testing would not be available to a participant or a participant's physician and would not alter participant care in any manner.

## Adverse event reporting

No adverse events are expected. The procedure of inserting the scope into the anal canal (HRA) may be embarrassing for some persons. The anal speculum can be uncomfortable, and the vinegar solution can cause some irritation in the anus. Some bleeding occurs with every biopsy. Serious bleeding is rare, about 1 in 1000 biopsies. If serious bleeding occurs, a simple procedure may be necessary to stop the bleeding such as burning or cauterizing the area. An injection of lidocaine may be given prior to a biopsy. It is possible to experience pain or dizziness from the injection. Rarely, an allergic reaction could occur. Events will be graded according to Common Terminology Criteria for Adverse Events v5 (CTCAE)

We will follow the Cancer Therapy Evaluation Program (CTEP) guidelines for reporting of adverse events (although we are employing no therapeutic interventions). Reportable safety events will be submitted to the MCW Institutional Review Board (IRB) per institutional guidelines. The study team, including PI, Study Coordinator, and other study staff will have weekly meetings. At each weekly meeting after enrollment starts, the Study Coordinator will provide the following information: number of participants entering the study, status with respect to meeting recruitment targets, the percentage of participants completing swab 1 and 2, number of drop-outs, reasons for drop-out, and number of participants undergoing HRA. Information about any adverse events also will be presented including potential anxiety from persistent HPV results or harm from directed biopsies. These participants will be managed using standard of care practices. By examining this information, the team will keep abreast of critical issues regarding recruitment and data integrity. Study staff also will notify at least one supervisor immediately if at any point a participant shows the need for urgent treatment (e.g., diagnosis of cancer). This type of information will be communicated immediately, with consultation with clinician co-Investigators about an appropriate course of action. In the event of an injury that results from the research, neither financial compensation nor the costs of medical treatment will be available through the research project. However, necessary facilities, emergency treatment, and professional services will be available to the participants, just as they are to the general community. Annual feedback will be provided to the NCI and MCW.

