# **Exclusion Criteria**

- Not acknowledge sex with men in the past five years and not identify as gay or bisexual
- Use of anticoagulants other than Aspirin or NSAIDS
- Prior diagnosis of anal cancer
- Plans to move within 12 months
- Not Milwaukee metro residents
- Not willing to attend one of the designated study clinics at baseline, or
- Inability to give informed consent.

Persons who have had HPV vaccination will not be excluded.

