#### HRA

All persons will receive HRA at the Anal Dysplasia Program of the Medical College of Wisconsin by a highly trained and experienced high-resolution anoscopist. A DARE will be done on all participants. For DARE and HRA, all findings will be recorded systematically. All suspicious lesions will be documented and biopsied. If no lesions are seen on HRA, then two biopsies will be taken from two different quadrants of the anal canal to support confirmation of the anoscopists' negative finding for lesions. A senior high-resolution anoscopist will observe the HRA and HRA-directed biopsies of the HRA clinician for 5 persons. We will also monitor HSIL rates, investigate unexpected variation in HSIL rates, and assesses need for further training and observations. Importantly, the primary outcomes for all 3 aims do not rely on HRA results. The clinician will also treat external anal disease or refer for treatment, triage internal anal disease if necessary, and ask to be notified if a participant has any anus-related concerns in the following week.

A blood draw will be done during the HRA visit. The blood specimen will allow testing for factors in serum, that may be associated with anal precancers.

For DARE and HRA follow up, persons will receive usual care. HBM constructs will then be used in a brief CASI focusing on the acceptability of HRA.

After the study is finished, we will telephone participants once a year for two years and ask about screening for anal cancer that the person may have done on their own and the results of that screening.

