# Pathology Readings

Biopsies specimens will be retained in the MCW Tissue Bank before forwarding to an MCW pathologist experienced in reading anal canal biopsies. The pathologist will use the most recent published criteria for describing the presence of dysplastic lesions.

Biopsies will be interpreted by a single experienced pathologist using a 2-tiered system (low-grade squamous intraepithelial lesion (LSIL) and high-grade squamous intraepithelial lesion (HSIL), and further classified by the applicable AIN subcategorization (anal intraepithelial neoplasia 1 (AIN1), AIN2 and AIN3). Low-grade AIN will be defined as the presence of AIN 1. High-grade AIN will be defined as the presence of AIN 2 or AIN 3. We plan to conduct p-16 staining on any histology samples that demonstrate a potential diagnosis for AIN 2/3. We anticipate 25% will need p-16 staining. The interpretation will drive clinical care and be available within 3 weeks of specimen collection. Biopsies will also be assessed for HPV genotypes.

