# Sample Size Estimation

Our Aim 1 outcome is compliance with swabbing at both baseline and 12 months. We will compare study arms using a Mantel-Haenszel test for difference in proportions in a stratified design. Assuming a large sample size in each arm (~200), we can approximate a lower bound for our

power assuming a chi-squared distribution with 1 degree of freedom. Given swab return data in cross-sectional studies, we anticipate ~80% of persons will return the home-based swab at baseline. Me estimate 10% loss to follow up at 12 months (n=180) and 80% of persons will return a home-collected swab (144) for 72% compliance at 12 months (i.e., 144/200).

Table 1. Power to detect difference in proportion of DNA samples received: home-based vs. clinic-based											
Proportion of home samples	Proportion of clinic samples	Difference	Power								
0.63	0.43	0.20	0.89								
0.72	0.54	0.18	0.84								
0.70	0.56	0.14	0.63								
0.65	0.52	0.13	0.55								

Using the same algorithm with cervical cancer screening compliance data,  $^{80}$  we estimate 70% of clinic-based attendees at baseline and 60% at 12 months also with 10% loss to follow up (200\*0.9 = 180; 180\*0.60 = 108 or 108/200 = 54% compliance). Using intent to treat, if 144 home-collected swabs (72%) and 108 clinic-collected swabs (54%) are returned at 12 months, and assuming two-sided tests and alpha of 0.05, we have 84% power to detect a difference (0.18) between arms (table 1) for Aim 1. Power was computed with PASS 14.

Aim 1 is the primary driver of the sample size of 400 which also provides ample power for assessing factors associated with compliance in Aim 2 as shown in table 2.

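### The adverse-event section anticipates no events, although its own bleeding figures imply them, and no active collection of delayed harm after biopsy is described

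*Combined protocol and SAP*

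**What the plan says.** The section on adverse event reporting begins "No adverse events are expected". The same paragraph goes on: "Some bleeding occurs with every biopsy. Serious bleeding is rare, about 1 in 1000 biopsies". It adds that a serious bleed may need a procedure to stop it, and it names discomfort, irritation from the acetic acid, pain or dizziness from the lidocaine injection, and rare allergic reaction. Events are to be graded by CTCAE v5, handled under CTEP reporting guidelines, sent to the IRB where reportable, and reviewed at weekly team meetings. Biopsy-related harm is named among the matters for those meetings.

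Every participant is to be scheduled for HRA at 12 months (Swabbing 2 at 12 months and HRA Scheduling). Suspicious lesions are biopsied, and a participant with no visible lesion has two biopsies (HRA section). Appendix V makes biopsy optional where only low-grade change is suspected. Afterwards the clinician will "ask to be notified if a participant has any anus-related concerns in the following week". A short post-HRA survey covers acceptability, including perceived pain (Computer-Assisted Self-Interviews). Of the biopsy reading, Pathology Readings says: "The interpretation will drive clinical care and be available within 3 weeks of specimen collection".

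The exclusion criteria list "Use of anticoagulants other than Aspirin or NSAIDS".

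**The concern.** There are two linked problems and one separate point.

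First, the opening sentence cannot stand beside the sentences that follow it. A study that biopsies most of those who attend HRA, including those without lesions, will by its own account produce some bleeding in everyone biopsied. Staff and readers should find one consistent statement of what is anticipated and how often.

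Second, the team undertakes to review biopsy harm weekly, but no described step gathers the delayed part of it in the same way from everyone. If reports depend on who makes contact, the count has no sound denominator. Few reports could then mean few events or few calls. Home- versus clinic-based screening is meant to lead on to HRA, so readers will want the harm of that step stated as a rate.

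Separately, anticoagulant use is checked as an entry criterion, while the biopsies come about 12 months later. The HRA scheduling text, the HRA section and Appendix V do not say whether the criterion still applies then.

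**Working it through.** **Inputs from the protocol**
- Serious bleeding per biopsy: p = 0.001 ("Serious bleeding is rare, about 1 in 1000 biopsies", Adverse event reporting).
- Minor bleeding per biopsy: 100% (same section).
- Participants: 400 ("Aim 1 is the primary driver of the sample size of 400").
- Loss to follow-up at 12 months: 10%, so 0.9 × 400 = 360 (Sample Size Estimation). People lost to follow-up are still to be approached for HRA, so 360 is a reference value and not a forecast.

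**Assumptions**
- HRA uptake: no expected value is given, because uptake is what Aim 3 estimates. I use 200 to 400 HRAs.
- Biopsies per HRA: two is the stated number when no lesion is seen. The number otherwise is not given, so I show one to three.
- Bleeds are independent across biopsies. If they cluster within participants, the expected count is unchanged and the chance of at least one is somewhat lower.

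**Formulas.** With n HRAs and k biopsies each, the number of biopsies is m = nk. The expected number of serious bleeds is 0.001 × m. The chance of at least one in the trial is 1 − 0.999^m. The protocol states no trial-level figure, so there is none to reproduce.

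| HRAs | Biopsies each | m | Expected serious bleeds | Chance of at least one |
|---|---|---|---|---|
| 200 | 1 | 200 | 0.20 | 18.1% |
| 200 | 2 | 400 | 0.40 | 33.0% |
| 200 | 3 | 600 | 0.60 | 45.1% |
| 360 | 1 | 360 | 0.36 | 30.2% |
| 360 | 2 | 720 | 0.72 | 51.3% |
| 360 | 3 | 1080 | 1.08 | 66.1% |
| 400 | 1 | 400 | 0.40 | 33.0% |
| 400 | 2 | 800 | 0.80 | 55.1% |
| 400 | 3 | 1200 | 1.20 | 69.9% |

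For one participant with two biopsies: 1 − 0.999² = 0.002, or 0.2%.

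**How each kind of harm reaches the study, on the supplied text**
- At the procedure: the clinician is present, findings are recorded systematically, and hemostasis is attended to before the anoscope is removed (HRA section; Appendix V).
- Perceived pain: asked in the post-HRA survey. When that survey is completed relative to the HRA is not stated.
- Delayed bleeding, infection or unplanned care: the only described route is the participant contacting the clinician within a week.
- The yearly telephone calls after the study ask about screening and its results.

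**The case against.** The strongest reply is that only one sentence is wrong. The list of events stands in the same paragraph, so anyone judging whether a bleed was anticipated has it to hand. A reader might infer that routine bleeding would be classed as unexpected. The documents do not support that: it would depend on how the cited reporting guidelines treat the sentence, and those are not reproduced.

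It is also fair to say that harms are not collected solely when volunteered. The clinician sees events at the visit, pain is asked about, and adverse events go to weekly review. Nor can one say that the post-HRA survey omits bleeding, because the appendix gives it by title only and the description in the text is a summary. Consent pages are not available either. The gap is therefore an absence from the supplied text, and it concerns delayed events.

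Harm is not an endpoint. Aim 3 is the proportion who agree to HRA, and the HRA section says that the primary outcomes do not rely on HRA results. No aim is damaged.

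On anticoagulants, the entry criterion and the HRA text do not contradict each other, since the latter is silent. The protocol gives no reason for the exclusion and no figure for how many participants might start such treatment during the year, so no count of people affected can be supported.

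All of this narrows the point. It does not remove the inconsistency, or the lack of a described step that asks everyone about delayed harm.

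**Conclusion.** The point holds in limited form. The opening sentence conflicts with the rest of its own section, and it would do so at any HRA uptake, because some bleeding is said to follow every biopsy. For serious bleeding, the trial should anticipate 0.4 to 0.8 events and a 33% to 55% chance of at least one, assuming 200 to 400 HRAs, two biopsies each and independence. With one to three biopsies each, the chance runs from 18% to 70%.

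A reader might take a figure near 1 in 2 as a participant's own risk. It is the chance of at least one event across the whole trial; the individual risk at two biopsies is about 0.2%. Nor is 55% an upper limit, since more biopsies per person would raise it.

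The second part is that delayed bleeding and unplanned care have no described active, timed collection, although weekly review of biopsy harm is promised. This affects how completely harm is ascertained and not the primary comparison. The anticoagulant point goes no further than a need to reconcile the entry criterion with the HRA text.

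**What to change.** 1. Replace the opening sentence of the adverse-event section with the anticipated events it already lists. Add the expected number of serious bleeds in the trial, with the assumed number of HRAs and biopsies beside it.
2. Ask every HRA participant the same short questions on bleeding, pain, infection and unplanned care since the procedure. Use the post-HRA survey if it is completed after the one-week window, and otherwise one brief scripted contact. The protocol says when the pathology reading will be available but describes no contact to convey it, so the plan should not rely on such a contact already existing.
3. Grade the answers by CTCAE, take them to the weekly meeting, and report them with the number of HRAs as denominator, together with the number who answered.
4. Have the clinical investigators reconcile the anticoagulant exclusion with the HRA scheduling text, the HRA section and Appendix V, stating whether the criterion still applies at HRA. No clinical rule is proposed here.

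The cost is protocol wording, a few questions, a little staff time and more low-grade events on record. Arms, endpoints and sample size do not change.

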#### Criteria for Termination of the Trial

Since there are only 2 visits and an HRA visit, the trial cannot be terminated until these activities have been completed. For example, a participant who is not compliant with a swabbing visit but does attend an HRA is an important data point for determining the primary outcome of compliance.

# APPENDICES

# APPENDIX I: STUDY SCHEDULE

Time table of activities																				$\neg$
Time table of activities	2017- 2018-			2019-				20	)20	)_		20	_	=						
				2019				2020				2021				2022				
(shaded blocks indicate the activity will	_		3		9			6	_	_	3		_			6		1	3	6
occur in that quarter)	1	2	_											2					-	-
	1	-	5	8	- 1	-	- 5	8	1	-	- 5	8	- 1	-	5	- 8	1	-	5	8
		2			1	2			1	2			1	2				2		
Complete human subjects' approvals																				
Transfer of grant from Houston to																				
Milwaukee																				
Install/meet with CAB to discuss																				
responsibilities																				
Edit/finalize protocol, interview questions,																				
home kit																				
Train/observe clinician staff in study																				
procedures																				
Pilot/analyze pilot/revise full protocol																				
Recruit participants and deliver protocol -																				
swab 1																				
Genotype first 200 specimens from time 0																				
Deliver protocol – swab 2; conduct HRAs																				
Genotype 200 specimens from time 0 and																				
200 from time 12																				
Perform epidemiological and statistical																				
analyses																				
Genotype last 200 specimens from time 12																				
Prepare and submit manuscripts																				

# APPENDIX IV: INSTRUCTION FOR CLINICAL SWABBING

Clinical anal canal swabbing will be performed at the Milwaukee clinics identified above. The participant should undress so that the buttocks are exposed, and either bend over the exam table or lay in the left lateral decubitus position. The examiner should use one hand to spread the buttocks and expose the anal verge.

